## 8.1.1 Adverse (Drug) Reaction

All noxious and unintended responses to a medicinal product related to any dose should be considered an adverse drug reaction. "Responses" to a medicinal product means that a causal relationship between a medicinal product and an adverse event is at least a reasonable possibility, ie, the relationship cannot be ruled out.

# 8.1.2 Unexpected Adverse Drug Reaction

An unexpected adverse drug reaction is defined as an adverse reaction, the nature or severity of which is not consistent with the applicable product information.

# 8.1.3 Assessment of Adverse Events by the Investigator

The Investigator will assess the severity (intensity) of each adverse event and will also categorize each adverse event as to its potential relationship to study drug.

The Investigator will assess all adverse events using the Common Terminology Criteria for Adverse Events (CTCAE) version 5.0 grading system.

## Assessment of severity

The severity of all adverse events should be graded according to the CTCAE. For those adverse event terms not listed in the CTCAE, the following grading system should be used:

- CTCAE Grade 1: Mild; asymptomatic or mild symptoms; clinical or diagnostic observations only; intervention not indicated
- CTCAE Grade 2: Moderate; minimal local or noninvasive intervention indicated; limiting age-appropriate instrumental activities of daily living
- CTCAE Grade 3: Severe or medically significant but not immediately life-threatening; hospitalization or prolongation of hospitalization indicated; disabling; limiting self-care activities of daily living
- CTCAE Grade 4: Life-threatening consequences; urgent intervention indicated
- CTCAE Grade 5: Death related to the adverse event

#### Causality assessment

The relationship of an adverse event to the administration of the study drug is to be assessed according to the following definitions:

No (unrelated, not related, unlikely to be related) – The time course between the administration of study drug and the occurrence or worsening of the adverse event rules out a causal relationship and another cause (concomitant drugs, therapies, complications, etc) is suspected.

Yes (possibly, probably, or definitely related) – The time course between the administration of study drug and the occurrence or worsening of the adverse event is consistent with a causal relationship and no other cause (concomitant drugs, therapies, complications, etc) can be identified.

The definition implies a reasonable possibility of a causal relationship between the event and the study drug. This means that there are facts (evidence) or arguments to suggest a causal relationship.

The following factors should also be considered:

• The temporal sequence from study drug administration-

The event should occur after the study drug is given. The length of time from study drug exposure to event should be evaluated in the clinical context of the event.

• Underlying, concomitant, intercurrent diseases-

Each report should be evaluated in the context of the natural history and course of the disease being treated and any other disease the patient may have.

Concomitant drug-

The other drugs the patient is taking or the treatment the patient receives should be examined to determine whether any of them might be recognized to cause the event in question.

• Known response pattern for this class of study drug-

Clinical and/or preclinical data may indicate whether a particular response is likely to be a class effect.

Exposure to physical and/or mental stresses-

The exposure to stress might induce adverse changes in the recipient and provide a logical and better explanation for the event.

• The pharmacology and PK of the study drug-

The known pharmacologic properties (absorption, distribution, metabolism, and excretion) of the study drug should be considered.

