## Source: Study NST-02 interim analysis (data on file) 1.4.1.3 Clinical safety

A safety review was performed of the 157 patients screened at the time of the Week 16 interim analysis with the treatment-emergent adverse events (TEAEs) presented in Table 2. There was no notable difference in the frequency, severity, or causality of the overall safety profile between placebo and either 300 mg or 600 mg of icosabutate for up to 16 weeks. The majority of TEAEs were mild to moderate in severity and generally comparable across the study arms. The treatment was well tolerated and comparable to placebo, with the exception of mild nausea (4.3%, 9.0%, and 21.3% in placebo, 300 mg, and 600 mg, respectively).

Table 2. Overview of TEAEs by Treatment Arm in Study NST-02

	Placebo (n=46)	Icosabutate 300 mg (n=46)	Icosabutate 600 mg (n=47)	
Any TEAE (n [%])	37 (80.4%)	30 (65.2%)	37 (78.75%)	
Maximum severity				
Grade 1 (n [%])	12 (26.1%)	7 (15.2%)	9 (19.1%)	
Grade 2 (n [%])	24 (52.2%)	22 (47.8%)	20 (42.6%)	
Grade 3 (n [%])	1 (2.2%)	1 (2.2%)	4 (8.5%)	
Grade 4 (n [%])	0 (0.0%)	0 (0.0%)	0 (0.0%)	
Grade 5 (n [%])	0 (0.0%)	0 (0.0%)	0 (0.0%)	
Drug-related TEAE (n [%])	7 (15.2%)	7 (15.2%)	8 (17.0%)	
SAE (n [%])	1 (2.2%)	1 (2.2%)	3 (6.4%)	
Drug-related SAE (n [%])	0 (0.0%)	0 (0.0%)	0 (0.0%)	
SAE = serious adverse event; TEAE = treatment-emergent adverse event. Source: Study NST-02 interim analysis (data on file)				

No confirmed drug-induced liver injury, cardiovascular events, or worsening of diabetes were observed during the study period. Laboratory values remained stable or improved and there were no clinically relevant changes in vital signs or electrocardiograms (ECGs). No safety or tolerability signals of concern were observed during the study period as confirmed by an independent unblinded DSMC review. In summary, the safety and tolerability of icosabutate remains favorable and similar to that observed in other patient populations.

ALP = alkaline phosphatase; ALT = alanine aminotransferase; ApoC3 = apolipoprotein C3; AST = aspartate aminotransferase; ELF = enhanced liver fibrosis; GGT = gamma glutamyl transferase; HbA1c = hemoglobin A1c; HDL-C = high-density lipoprotein-cholesterol; HOMA-IR = Homeostatic Model Assessment of Insulin Resistance; hsCRP = high-sensitivity C-reactive protein; LDL-C = low-density lipoprotein-cholesterol; Pro-C3 = N-terminal type 3 collagen propeptide; TG = triglyceride.

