# 8.3 Serious Adverse Event Reporting – Procedures for Investigators

## **Initial reports**

All SAEs occurring from the time of informed consent until 30 days following the last dose of study drug must be reported to Medpace Clinical Safety within 24 hours of the knowledge of the occurrence. After the 30-day reporting window, any SAE that the Investigator considers related to study drug must be reported to the Medpace Clinical Safety or Sponsor designee.

To report the SAE, complete the SAE form electronically in the Electronic Data Capture (EDC) system for the study. When the form is completed, Medpace Safety personnel will be notified electronically by the EDC system and will retrieve the form. If the event meets serious criteria and it is not possible to access the EDC system, send an email to Medpace Safety at [contact] or call the Medpace SAE reporting line (phone number listed below), and fax/email the completed paper SAE form to Medpace (contact information listed in Section 8.6) within 24 hours of awareness. When the EDC system becomes available, the SAE information must be entered within 24 hours of the system becoming available.

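### The two causality categories in Protocol 8.1.3 leave some adverse events in neither, and the related category is narrower than the reaction standard in 8.1.1

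*Protocol*

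**What the plan says.** Protocol 8.1.1 treats a response as an adverse drug reaction when the causal link "is at least a reasonable possibility, ie, the relationship cannot be ruled out".

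Protocol 8.1.3, under Causality assessment, gives the investigator two categories:

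- *No* applies when the time course "rules out a causal relationship and another cause (concomitant drugs, therapies, complications, etc) is suspected".
- *Yes*, labelled "Yes (possibly, probably, or definitely related", applies when the time course "is consistent with a causal relationship and no other cause (concomitant drugs, therapies, complications, etc) can be identified".

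The same section then says that the definition implies a reasonable possibility, and adds: "This means that there are facts (evidence) or arguments to suggest a causal relationship". A list of factors to weigh follows, among them underlying disease and other drugs.

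Neither document says how to code an event that meets neither definition. SAP 3.6.1 tabulates drug-related TEAEs and drug-related serious TEAEs without defining relatedness again. SAP 3.1.6 imputes nothing for missing safety data.

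**The concern.** Each category joins two conditions with *and*, so together they cannot cover every event. The gap falls where this population will often sit. Enrolled patients have NASH, many will have diabetes or lipid disorders, and Protocol 5.6.2 allows background antidiabetic and lipid-lowering drugs. An event with plausible timing will often have another candidate explanation. The form then offers no category that fits, although 8.1.1 points to a reaction.

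Three outputs depend on the answer:

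- the drug-related TEAE and serious TEAE summaries (Protocol 9.2.2, SAP 3.6.1);
- the investigator's contribution to deciding whether a serious event is a suspected reaction (Protocol 8.5);
- SAE reporting once 30 days have passed since the last dose, when "any SAE that the Investigator considers related to study drug must be reported" (Protocol 8.3).

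If sites resolve the gap differently, identical events will be coded differently, and the related-event tables will partly reflect site habit.

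**Working it through.** The plan gives no figure on this point to reproduce. The check is to enumerate the combinations and compare the two standards.

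**Step 1. Classify each combination.** The inputs are the *Yes* and *No* definitions in 8.1.3 and the reaction standard in 8.1.1. Another cause here means one that is possible, not one already shown to be the sole explanation.

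| Row | Timing | Another possible cause | 8.1.3 category | Reaction under 8.1.1 |
|---|---|---|---|---|
| 1 | excludes causality | yes | *No* | no |
| 2 | excludes causality | no | neither | no |
| 3 | consistent | yes | neither | yes |
| 4 | consistent | no | *Yes* | yes |

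Two of the four rows have no category. Row 3 matters for the related-event count. Row 2 shows that the *No* definition is incomplete as well.

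**Step 2. Compare the counts.** Let n3 and n4 be the numbers of events in rows 3 and 4.

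- Reactions under 8.1.1: n3 + n4.
- *Yes* under a literal reading of 8.1.3: n4.
- If sites code a fraction q of row 3 events as *Yes*, the recorded count is n4 + q × n3.
- Shortfall against 8.1.1: (n3 + n4) − (n4 + q × n3) = (1 − q) × n3.

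The shortfall runs from 0 (q = 1) to n3 (q = 0). The documents give neither n3 nor q, so its size cannot be calculated.

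**Step 3. Compare 8.1.3 with itself.** A *Yes* that includes possibly related events, and that rests on facts or arguments suggesting causality, would take in row 3. A *Yes* that requires that no other cause be identifiable would not. Both statements stand in one section, with no order of precedence.

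**Step 4. See whether the interim data settle it.** Protocol 1.4.1.3 reports "mild nausea (4.3%, 9.0%, and 21.3% in placebo, 300 mg, and 600 mg, respectively". Its Table 2 gives patients with any drug-related TEAE as 7/46, 7/46 and 8/47 (15.2%, 15.2%, 17.0%).

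- Assume that the nausea percentages use the Table 2 denominators. Placebo fits (2/46 = 4.3%) and 600 mg fits (10/47 = 21.3%). The 300 mg figure does not: 4/46 = 8.7% and 5/46 = 10.9%, and neither is 9.0%.
- Maximum-severity grades in Table 2 add up to the any-TEAE count for placebo (12 + 24 + 1 = 37) and 300 mg (7 + 22 + 1 = 30). For 600 mg they give 9 + 20 + 4 = 33 against 37, so that column does not agree with itself.

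On the same assumption, about 10 patients at 600 mg had nausea and 8 had any related event, so at least 10 − 8 = 2 nausea patients had no event scored as related. That is compatible with a restrictive rule. It is also what blinded investigators might record under any definition.

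**The case against.** The strongest defence is that 8.1.3 should be read as a whole. Its label, the reasonable-possibility sentence and the list of factors all point to the 8.1.1 standard, and a sensible investigator would code a row 3 event as *Yes*. This stands in part: it is why a shortfall cannot be assumed. It does not remove the defect, because the later text conflicts with the requirement that no other cause be identifiable and never says which category an unplaced event takes.

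It is also fair that much of the safety reporting does not turn on relatedness:

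- all SAEs up to 30 days after the last dose are reported (8.3);
- suspected drug-induced liver injury is an AESI, sent on an SAE form within 24 hours whether or not it is serious (8.1.4);
- the Appendix E liver actions are set by laboratory values and symptoms;
- all TEAEs are tabulated by arm regardless of cause;
- in the withdrawal criterion of 4.3, relatedness is one alternative beside the investigator's judgement of the patient's interest.

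This stands, and it limits the exposure to the three outputs named above.

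A reader might infer three stronger things that the documents do not support:

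- *Related events are in fact under-counted.* A row 3 event fails *No* as plainly as it fails *Yes*, and nothing says which one sites choose.
- *The nausea pattern proves it.* The 300 mg percentage matches no count out of 46, the 600 mg column of Table 2 is inconsistent, and the rule is not the only explanation.
- *The comparison is biased toward no difference.* If a strict rule captures the same fraction s of related events in every arm, the risk difference shrinks to s × (p1 − p0), but the ratio p1/p0 is unchanged. A broader rule also admits background events in all arms, which can dilute the contrast.

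**Conclusion.** The point holds as an internal contradiction in the definitions. Section 8.1.3 leaves two of four combinations unclassified. Its *Yes* definition is a strict subset of the 8.1.1 standard, and it conflicts with its own label and explanatory text.

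The consequence is a risk: drug-related events may be under-counted relative to 8.1.1, or coded inconsistently between sites. Under-counting depends on investigators applying the definition literally, which the documents neither confirm nor exclude. The size is unknown.

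The histological primary endpoint, eligibility and sample size are untouched. The wording should be corrected, but it does not threaten the main efficacy conclusion or the all-cause safety tables.

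**What to change.** Reconcile 8.1.3 with 8.1.1 so that every event falls into exactly one category, on the standard the protocol already states:

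- *Yes*: there is a reasonable possibility of a causal relationship that cannot be excluded, even if another cause is also possible.
- *No*: there is no reasonable possibility of a causal relationship.

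Put the same wording in the eCRF completion guidelines.

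If existing *No* assessments are re-queried, do it blinded and before database lock, since SAP 5.2 unblinds after lock. Apply one rule, such as consistent timing, to all event terms or to all SAEs and AESIs. Do not start from nausea or any other term picked from interim results by arm: those rates are printed in the protocol, and choosing a term by its known dose pattern would bring in bias even with patient-level blinding intact. If the protocol text can no longer be amended, state in the clinical study report which rule was applied.

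The cost is one paragraph of wording, the guideline text, site queries, and a somewhat higher drug-related rate in all arms.

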# 8.1.4 Adverse Events of Special Interest

The Investigator will monitor each patient for clinical and laboratory evidence of predefined adverse events of special interest (AESIs) throughout the patient's participation in this study.

Events of suspected drug-induced liver injury will be monitored as AESIs during this study. During the course of the study, additional AESIs may be identified by the Sponsor.

The Investigator will assess and record in detail any additional information on AESIs on an SAE form (whether or not the event meets seriousness criteria in Section 8.2), to be submitted within 24 hours of awareness of the event. Adverse events of special interest must be recorded on the eCRF.

#### 8.2 Serious Adverse Events

An adverse event or adverse reaction is considered serious if, in the view of either the Investigator or Sponsor, it results in any of the following outcomes:

- Death.
- A life-threatening adverse event.

Note: An adverse event or adverse reaction is considered "life-threatening" if, in view of either the Investigator or Sponsor, its occurrence places the patient at immediate risk of death. It does not include an event that, had it occurred in a more severe form, might have caused death.

• Requires hospitalization or prolongation of existing hospitalizations.

Note: Any hospital admission with at least 1 overnight stay will be considered an inpatient hospitalization. An emergency room or urgent care visit without hospital admission will not be recorded as an SAE under this criterion, nor will hospitalization for a procedure scheduled or planned before signing the ICF, or elective treatment of a preexisting condition that did not worsen from baseline. However, unexpected complications and/or prolongation of hospitalization that occur during elective surgery should be recorded as adverse events and assessed for seriousness. Admission to the hospital for social or situational reasons (ie, no place to stay, live too far away to come for hospital visits, respite care) will not be considered inpatient hospitalizations.

- A persistent or significant disability/incapacity or substantial disruption of the ability to conduct normal life functions.
- A congenital anomaly/birth defect.
- An important medical event.

Note: Important medical events that do not meet any of the above criteria may be considered an SAE when, based upon appropriate medical judgment, they may jeopardize the patient and may require medical or surgical intervention to prevent one of the outcomes listed above. Examples of such medical events include allergic bronchospasm requiring intensive treatment in an emergency room or at home, blood dyscrasias or convulsions that do not result in inpatient hospitalizations, or the development of drug dependency.

# 8.3 Serious Adverse Event Reporting – Procedures for Investigators

## **Initial reports**

All SAEs occurring from the time of informed consent until 30 days following the last dose of study drug must be reported to Medpace Clinical Safety within 24 hours of the knowledge of the occurrence. After the 30-day reporting window, any SAE that the Investigator considers related to study drug must be reported to the Medpace Clinical Safety or Sponsor designee.

To report the SAE, complete the SAE form electronically in the Electronic Data Capture (EDC) system for the study. When the form is completed, Medpace Safety personnel will be notified electronically by the EDC system and will retrieve the form. If the event meets serious criteria and it is not possible to access the EDC system, send an email to Medpace Safety at [contact] or call the Medpace SAE reporting line (phone number listed below), and fax/email the completed paper SAE form to Medpace (contact information listed in Section 8.6) within 24 hours of awareness. When the EDC system becomes available, the SAE information must be entered within 24 hours of the system becoming available.

## Follow-up reports

The Investigator must continue to follow the patient until the SAE has subsided or until the condition becomes chronic in nature, stabilizes (in the case of persistent impairment), or the patient dies.

Within 24 hours of receipt of follow-up information, the Investigator must update the SAE form electronically in the EDC system for the study and submit any supporting documentation (eg, patient discharge summary or autopsy reports) to Medpace Clinical Safety via fax/email. If it

is not possible to access the EDC system, refer to the procedures outlined above for initial reporting of SAEs.

# 8.4 Pregnancy Reporting

If a patient becomes pregnant during the study or within the safety follow-up period (ie, prior to the Safety Follow-up Visit), the Investigator is to stop dosing with study drug(s) immediately, and the patient should be withdrawn from the study. Early termination procedures should be implemented at that time.

A pregnancy is not considered to be an adverse event or SAE; however, it must be reported to Medpace Clinical Safety within 24 hours of knowledge of the event. Medpace Clinical Safety will then provide the Investigator/site the Exposure In Utero (EIU) form for completion. The Investigator/site must complete the EIU form and fax/email it back to Medpace Clinical Safety.

If the female partner of a male patient becomes pregnant while the patient is receiving study drug or within the safety follow-up period, the Investigator should notify Medpace Clinical Safety as described above.

The pregnancy should be followed until the outcome of the pregnancy, whenever possible. Once the outcome of the pregnancy is known, the EIU form should be completed and faxed/emailed to Medpace Clinical Safety. If the outcome of the pregnancy meets the criteria for immediate classification as an SAE (ie, postpartum complication, spontaneous abortion, stillbirth, neonatal death, or congenital anomaly), the Investigator should follow the procedures for reporting an SAE.

# 8.5 Expedited Reporting

The Sponsor/designee will report all relevant information about Suspected Unexpected Serious Adverse Reactions (SUSARs) that are fatal or life-threatening as soon as possible to the Food and Drug Administration, and in any case no later than 7 days after knowledge by the Sponsor/designee of such a case. Relevant follow-up information will subsequently be communicated within an additional 8 days.

All other SUSARs will be reported to the Food and Drug Administration as soon as possible but within a maximum of 15 days of first knowledge by the Sponsor/designee.

The Sponsor/designee will also report any additional expedited safety reports required in accordance with the timelines outlined in country-specific legislation.

The Sponsor/designee will also inform all Investigators as required per local regulation.

The requirements above refer to the requirements relating to investigational medicinal products.

# **8.6** Special Situation Reports

Special situation reports include reports of overdose, misuse, abuse, medication error, and reports of adverse reactions associated with product complaints.

- Overdose: Refers to the administration of a quantity of a medicinal product given per administration or cumulatively (accidentally or intentionally), which is above the maximum recommended dose according to the protocol. Clinical judgment should always be applied. In cases of a discrepancy in the study drug accountability, overdose will be established only when it is clear that the patient has taken additional dose(s) or the Investigator has reason to suspect that the patient has taken additional dose(s).
- **Misuse:** Refers to situations where a medicinal product is intentionally and inappropriately used in a way that is not in accordance with the protocol instructions or local prescribing information and may be accompanied by harmful physical and/or psychological effects.
- **Abuse:** Is defined as persistent or sporadic, intentional excessive use of a medicinal product, which is accompanied by harmful physical or psychological effects.
- **Medication error:** Is any unintentional error in the prescribing, dispensing, or administration of a medicinal product by a healthcare professional, patient, or consumer, respectively. The administration or consumption of the unassigned treatment and administration of an expired product are always reportable as medication errors. Cases of patients missing doses of investigational product are not considered reportable as medication errors.

All special situation events as described above must be reported on the Special Situations Report form and faxed/emailed to Medpace Clinical Safety (contact information listed below) within 24 hours of knowledge of the event. All adverse events associated with these Special Situation Report forms should be reported as adverse events or SAEs, as well as recorded on the adverse event eCRF and/or the SAE report form. Details of the symptoms and signs, clinical management, and outcome should be provided, when available.

Safety Contact Information: Medpace Clinical Safety

Medpace SAE reporting line – USA:

[contact], dial 3 or [contact], dial 3

[contact] or [contact]

Email: [name] [contact]

